A study carried out by Bendstrup, et al (2002),¹⁷ evaluated the effects of the inhibition of systemic coagulation through nebulized unfractionated heparin at doses up to 64 mg and identified that there is a dose-dependent effect for factor Xa inactivation, inducing minimal changes in aPTT, and it is safe for clinical or research purposes, without increasing the risk of bleeding.¹⁸

Phelps, et al (2020),¹⁹ carried out a systematic review on the use of UFH inhalation for the treatment of inhalation injury caused by heat in burn patients and concluded that nebulized heparin did not demonstrate an increase in the risk of bleeding rates and decreased the duration of mechanical ventilation.

For COVID-19, the heparin anti-viral effect is expected to be related to the fact that heparin blocks viral interaction with host receptors thereby inhibiting virus interaction with the cell and, consequently, viral invasion.^{20, 21} To this moment, some studies indicate that treatment with systemic heparin reduced hospital mortality in patients with COVID-19²² and a previous study that strongly supported the clinical investigation of heparin as a potential treatment for patients with COVID-19,^{23, 24} justifies further investigation to prove these clinical effects.

Objectives

Primary objectives assessment

Safety: related to the use of nebulized enriched heparin by patients with SARS-CoV-2 through the assessment of hemorrhagic events of any nature, alteration of the coagulation testing, like prolonged activated partial thromboplastin time (aPTT), indicated by an increase in aPTT>1.5, and heparin-induced thrombocytopenia; Efficacy: related to the proposed treatment, through analysis of the SARS-CoV-2 viral load of the participants treated by the sequential assessment of reverse transcription-polymerase chain reaction (RT-PCR) in the nasal swab.

Secondary objectives assessment

Safety measured by respiratory, clinical, laboratorial and tomographic findings as follows, in number of patients, and hospitalization days:

Supplemental oxygen therapy needed;

Mechanical pulmonary ventilation needed;

Renal failure development;

Development of major cardiovascular events such as pulmonary embolism and acute myocardial infarction;

Demand for intensive care unit (ICU) treatment;

Secondary pulmonary bacterial infections (bacterial pneumonia);

Deep vein thrombosis (DVT) through Doppler ultrasonography assessment;

Pancreatitis characterized by increase in amylase >200 U/L;

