Demand for corticosteroid therapy such as hydrocortisone, dexamethasone and other corticosteroids due to inflammatory pulmonary disease;

Death;

Increase in white blood cell count (>10.000 cells/mm³);

Increase in C reactive protein test (CRP) (>3.00mg/L);

Deterioration of arterial blood gas paO₂/pFiO₂ ratio (<200);

Altered sodium (< 135mEq/L or > 145mEq/L);

Altered potassium (< 3,5mEq/L or > 5,5mEq/L);

Worsening of pulmonary area compromised (%) by inflammation or infection through tomographic assessment.

Method

EnHanCed study design

The present protocol refers to a phase I / II, prospective, randomized, parallel, triple blind clinical trial. This design is justified by the lack of a drug-specific cost-efficient treatment for SARS-CoV-2 patients. The use of a therapeutic drug justifies the need for a placebo control group. A minimum number of participants will be allocated to this study, as the main intention will be to evaluate the safety of the treatment. Triple blind clinical studies have the lowest levels of bias and, therefore, the highest level of evidence for a clinical study. It is understood that there is no need for a purely phase I study based on the literature data previously presented.

The study will be carried out at the São Paulo State University (UNESP) Clinical Hospital of the Botucatu Medical School, Botucatu, São Paulo, Brazil.

Dosage and administration

Considering the pulmonary water loss of 8 to 10mL during the gas exchange in 30 minutes (of inhalation) and compensating the dilution of the solution in the pulmonary fluids, we opted for the dose of 2.5 mg heparin in 10mL of 0.9% saline solution, aiming the effective mean tested doses (62.5 μ g/mL to 250 μ g/mL), nebulized 4/4 hours, except the nebulization that would be administered between 12 pm and 6 am. The treatment will be administered for 7 days because it will be assumed that the reduction in viral load promoted by enriched heparin will have a significant impact during the first 14 days of the infectious process. Considering that the patient has already had the disease for at least seven days when admitted and that the viral load tends to reduce spontaneously after the referred period, it is known that complications persist due to other factors such as inflammatory response.

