The total recruitment size will be 50 participants, aiming at 40 patients followed during the study period. The sample was estimated considering the number of patients diagnosed as COVID-19 at the São Paulo State University (UNESP) Clinical Hospital that met the study's eligibility criteria.

The sample calculation of 40 patients took into account two independent study arms, with an estimated proportion in the viral load reduction rate of 30% for group 1, that will receive placebo, and 75% for group 2 that will be treated with enriched nebulized heparin as proposed in this study, considering 80% test power and a 5% significance level for a bilateral test.

Categorical variables will be evaluated with Fisher's exact test, continuous variables will be compared with non-parametric methods such as Mann-Whitney test or U test, paired comparisons will be evaluated with the Wilcoxon test, multivariate analyzes will be evaluated with regression Cox analysis and long-term clinical analyzes will be compiled on Kaplan-Meir curves.

Interventions and inpatient schedule

Intervention	Day 0	Day 1	Day 2	Day 3	Day 4	Day 5	Day 6	Day 7	Day 8
Informed consent form	X								
Medical visit, patient story and physical examination	X	X	X	X	X	X	X	X	X
Vital signs assessment	X	X	X	X	X	X	X	X	X
Medications in use	X	X	X	X	X	X	X	X	X
Inclusion and exclusion criteria	X								
COVID-19 viral load in RT-qPCR	X		X			X		X	X
Complete blood count, D-dimer, aPTT, urea, creatinine, glucose, reactive protein C, blood gas and amylase	X		X			X		X	X
Computed thoracic tomography	X								X
HMWH or placebo administration		X	X	X	X	X	X	X	X
Adverse events	X	X	X	X	X	X	X	X	X
Discontinuation criteria	X	X	X	X	X	X	X	X	

Table 1. Schedule for assessments and intervention. The participants will be followed up and evaluated on days 0, 1, 2, 3, 4, 5, 6, 7 and 8 days after randomization.

The closure assessment will be carried out on day 8. Extra data can be collected if the patient's clinical condition changes. Randomization will be performed in up to 24 hours after admission. After the end of the study, the participant will be referred and accompanied at the COVID-19 outpatient clinic São Paulo State University (UNESP) Clinical Hospital.

Adverse events

Adverse effects related to the nebulized use of heparins will be tracked and analyzed according to the Common Terminology Criteria for Adverse Events (CTC-AE 5.0),²⁵ and will be graded from 1 to 5, accordingly to the severity of the event.

Grade	Description

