Aphasia	Yes 	No 	
Aphasia start date (blank if not present)			
Aphasia end date (blank if still present)			
Hyporexia	Yes 	No 	
Hyporexia start date (blank if not present)			
Hyporexia end date (blank if still present)			
Heart rate (BPM)			

Brachial systolic pressure (mmHg)					
Brachial diastolic pressure (mmHg)					
Peripheral oxygen saturation (%)					
Axillary temperature (Celsius)					
Paleness	Normal 	1+/4+ 	2+/4+ 	3+/4+ 	4+/4+ 
Cyanosis	Normal 	1+/4+ 	2+/4+ 	3+/4+ 	4+/4+ 
Oral cavity	Normal 	Altered 			
Description					
Pulmonary auscultation	Normal 	Altered 			
Description					
Cardiac auscultation	Normal 	Altered 			
Description					
Abdominal examination	Normal 	Altered 			
Description					
Limbs (pulses, edema, skin conditions)	Normal 	Altered 			
Description					

Figure 2. Clinical assessment and physical examination form based on SARS-CoV-2 most prevalent symptoms.

Laboratory results and tomographic findings form			
Form Number:	Date:		
RT-qPCR	Positive 	Negative 	
RT-qPCR quantitative viral load			
Blood count	Normal 	Altered 	
Hemoglobin (g / dL)			
Hematocrit (%)			
Mean corpuscular volume (fL)			
Red cell distribution width (%)			
Platelets count (10³ / µL)			
White cell count (10³ / µL)			
Neutrophils (%)			
Lymphocytes (%)			
Bands (%)			
Arterial gas	Normal 	Altered 	
pH			
pCO₂ (mmHg)			
PaO₂ / FiO₂			
HCO₃ (mEq / L)			
SO₂ (%)			
Base Excess			
D-Dimer (µg / mL)			
aPTT	Normal 	Altered 	
Prothrombin time (PT)			
International normalized ratio (INR)			
Activated partial thromboplastin time (aPTT)			
Normalized aPTT Ratio			
Renal function	Normal 	Altered 	
Urea (mg / dL)			
Creatinine (mg / dL)			

Fasted glucose (mg / dL)	
C reactive protein (CRP) (mg / L)	
Amylase (U / L)	
Thoracic tomography description	

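### The secondary outcome named pancreatitis is met by an amylase threshold alone, so an isolated enzyme rise would be tabulated as a disease event

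*Combined protocol and SAP*

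**What the plan says.** The protocol's section on secondary objectives opens with "Safety measured by respiratory, clinical, laboratorial and tomographic findings as follows, in number of patients, and hospitalization days". One item on that list is "Pancreatitis characterized by increase in amylase >200 U/L". Nothing further is attached to it: no sign or symptom, repeat value, imaging, clinician's diagnosis or adjudication.

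Two kinds of neighbouring item are worded differently. A diagnosis on the same list is tied to a procedure: "Deep vein thrombosis (DVT) through Doppler ultrasonography assessment". The laboratory thresholds are named as laboratory findings, for example "Increase in white blood cell count (>10.000 cells/mm³"; CRP is likewise called an increase, and sodium and potassium are called altered.

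Table 1 (Interventions and inpatient schedule) has one row for "Complete blood count, D-dimer, aPTT, urea, creatinine, glucose, reactive protein C, blood gas and amylase", marked on Days 0, 2, 5, 7 and 8. The only scheduled imaging is "Computed thoracic tomography", on Days 0 and 8. Physical examination is scheduled every day. Its form (Figure 2) has an item "Abdominal examination" scored normal or altered with free text, which the pancreatitis item does not use. The adverse events form has no pancreatitis line, but it has three free-text lines for other events, each with a grade from 1 to 5.

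**The concern.** A safety table built from this list would carry a row headed pancreatitis whose entries are patients with a raised enzyme. A reader takes such a row as a count of disease, but the rule counts threshold crossings. The two agree only if every crossing reflects the disease, and nothing in the plan checks that.

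The word for an increase is also unresolved. It could mean any value above 200 U/L, a crossing from at or below 200 on Day 0, or any rise that ends above 200. Day 0 amylase is drawn, but the plan does not say how it enters the definition.

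This deserves a correction because the study design section says the trial is kept small and aimed mainly at safety. In arms of about 20, one or two relabelled laboratory values make a visible percentage against a serious-sounding diagnosis.

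**Working it through.** The plan states no expected rate or calculation for this outcome, so there is no figure of its own to reproduce. The check has a textual part and an arithmetic part.

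**1. Text: what each item requires**

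| Item on the secondary list | Label | What meets it |
|---|---|---|
| White cells, CRP, sodium, potassium | laboratory change | threshold |
| Deep vein thrombosis | diagnosis | Doppler ultrasonography |
| Pancreatitis | diagnosis | amylase threshold only |

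Pancreatitis is the only diagnosis on the list defined by a blood-test threshold alone. The schedule does not supply the missing confirmation: amylase is the only pancreatic enzyme in the panel and on the laboratory form (Figure 3), and the scheduled tomography is thoracic. There are four draws after baseline (Days 2, 5, 7, 8). Since no repeat is required, one of them above 200 U/L is enough.

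**2. Weight of one patient**

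- Patients followed: 40 (Sample size, recruiting and statistical analysis). Allocation: 1:1 (Randomization and study arms). Per arm: 40/2 = 20.
- One patient: 1/20 = 5 percentage points. Two patients: 2/20 = 10 points.
- If all 50 recruited patients were counted: 1/25 = 4 points.

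**3. Chance of at least one enzyme-only case**

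Let q be the probability that a patient has an amylase value above 200 U/L without pancreatitis during follow-up. The documents give no value, so q is assumed over a range, with patients independent. For n patients, the chance of at least one such case is 1 − (1 − q)^n.

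| Assumed q | Expected cases per arm (20q) | At least one in an arm (n = 20) | At least one in the trial (n = 40) |
|---|---|---|---|
| 1% | 0.2 | 1 − 0.99^20 = 18% | 1 − 0.99^40 = 33% |
| 3% | 0.6 | 1 − 0.97^20 = 46% | 1 − 0.97^40 = 70% |
| 10% | 2.0 | 1 − 0.90^20 = 88% | 1 − 0.90^40 = 99% |

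**4. Effect on the between-arm test**

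The plan uses Fisher's exact test for categorical variables. For 2/20 against 0/20, the two-sided p is 2 × C(20,2)/C(40,2) = 2 × 190/780 = 0.49. A couple of relabelled cases would therefore not produce a significant difference. The harm lies in the label and the reported rate.

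**The case against.** The best defence is that the threshold is printed in the outcome's own wording, under an introduction that includes laboratory findings, so an attentive reader can see what was counted. The rule applies equally to both randomised, blinded arms and does not favour either. The item is secondary: the primary safety outcomes are haemorrhage, aPTT prolongation and heparin-induced thrombocytopenia. All of this stands and limits the point to labelling and interpretation. It does not make the row's title correct, and equal application to both arms does not make the rate in either arm a rate of pancreatitis.

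Several stronger readings are tempting, and the documents do not support them:

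- **That a patient with renal failure and raised amylase is wrongly counted twice.** The list counts patients item by item and defines no composite or total, so appearing under two items is not an error. No section links renal function to amylase.
- **That clinically diagnosed pancreatitis with amylase below 200 U/L would be lost.** It would not meet the listed item. But the plan allows extra data when a patient's condition changes, adverse events are assessed every day, and the free-text graded lines can hold the event.
- **That false cases are likely enough to mislead the safety conclusion or implicate one arm.** The 46% and 88% figures are only as good as the assumed rates, 1% gives 18%, and two cases against none gives p = 0.49.
- **That the protocol says a single value suffices.** It does not say so; it merely requires no second one.

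**Conclusion.** The point holds as a matter of outcome definition: a disease is named, a laboratory threshold is counted, and the Day 0 value has no stated role. Each isolated rise would add 5 percentage points to an arm's pancreatitis rate at 20 per arm. How often that would happen cannot be learned from the documents. The range of 18% to 88% for at least one such case per arm rests entirely on assumed rates of 1% to 10% and on independence between patients. The result is also conditional: if no isolated rise occurs, the row does no harm.

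This is a minor improvement. It changes what one row of the secondary safety table can be taken to mean, and leaves the primary safety outcomes, the efficacy analysis and the sample size untouched.

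**What to change.** 1. Rename the item *amylase >200 U/L, not present on Day 0* and report it as a laboratory outcome beside white cells and CRP. State how many patients were already above 200 U/L on Day 0.
2. Report pancreatitis separately, only when diagnosed by the clinicians under criteria that the investigators set and write down beforehand, whatever the amylase value. Record it with a grade on the existing lines for other adverse events.

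Merely combining the amylase threshold with an altered abdominal examination is not recommended. That form item is a non-specific normal/altered score, the combination would still leave out diagnosed cases at or below 200 U/L, and the choice of diagnostic criteria belongs to the investigators.

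The cost is a change of outcome wording and a short written criterion. Amylase values, including Day 0, and the adverse-event lines are already in the plan, so no visit, test or participant is added. The downside is that fewer events will be called pancreatitis.

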Individual vials containing 10 mL of enriched heparin (250 μ g/mL, that will be adjusted after the filtration process based on the result of biochemical analysis) or placebo (adding to the same total volume of 0.9% saline solution) will be prepared by the pharmacist, stored in a freezer at -30° Celsius, and delivered to the research team in a blind character. After receiving the preparation (enriched heparin or placebo), it must be inserted into the nebulizer cup and administered in a source of oxygen or compressed air (5L/min or according to the patient's need) in isolated rooms, a process that spend 30 minutes. Nebulization therapy will be performed after isolation of the patient and with support from the hospital infection control committee, so that there will be no greater risk of spreading the virus.

Eligibility criteria

Sign and agree to the free and informed consent form;

Both sexes, of any ethnic origin, aged between 18 and 90 years;

COVID-19 infected, diagnosed by reverse-transcriptase polymerase chain reaction (RT-PCR) or with a strong suspicion of COVID-19 through compatible clinical and radiological findings;

Time of disease evolution less than 10 days;

Radiological diagnosis of grade IIA pneumonia, with gas exchange ratio >200 in blood gas analysis (paO₂ / pFiO₂), characterizing mild hypoxemia;

Indication of hospital treatment regime, provided that the period of hospitalization before inclusion is not more than 24 hours;

Demand for supplemental oxygen therapy (O₂) less than 5 L/min.

Exclusion criteria

Disagree with the terms of the study;

Moderate or severe respiratory failure requiring ICU admission requiring invasive mechanical ventilation or positive pressure non-invasive ventilation (NIV);

Pregnancy or puerperium;

Hematological diseases;

Coagulation disorders;

Previous use of anticoagulants in therapeutic dosages for more than 72 hours;

Previous heparin-induced allergy or thrombocytopenia or current thrombocytopenia with a count of less than 50,000 platelets/mm³.

Discontinuation criteria

Participants can withdraw from the study, if they wish, at any time and regardless of the reason, without consent of the research team. Any type of severe adverse events, according to the rules of the Common Terminology Criteria for Adverse Events (CTC-AE 5.0)²⁵ will be considered criteria for discontinuation.

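### The CRP and white cell increase outcomes are fixed cut-offs with no Day 0 reference and no visit rule, so a literal count would be diluted by patients already abnormal at entry

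*Combined protocol and SAP*

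**What the plan says.** The list under Secondary objectives assessment is introduced by "Safety measured by respiratory, clinical, laboratorial and tomographic findings as follows, in number of patients, and hospitalization days", so its items are counted by patient. Two of them are "Increase in C reactive protein test (CRP) (>3.00mg/L" and "Increase in white blood cell count (>10.000 cells/mm³". Each consists of the word increase and an absolute value.

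Under Eligibility criteria, every participant has "Radiological diagnosis of grade IIA pneumonia, with gas exchange ratio >200 in blood gas analysis" and an indication for hospital treatment. No criterion limits CRP or white cell count at entry.

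Table 1 schedules "Complete blood count, D-dimer, aPTT, urea, creatinine, glucose, reactive protein C, blood gas and amylase" on Days 0, 2, 5, 7 and 8, and dosing starts on Day 1. The laboratory form records both markers as numbers.

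The section Sample size, recruiting and statistical analysis gives Fisher's exact test for categorical variables, Mann-Whitney for continuous variables and Wilcoxon for paired comparisons. It ties none of them to CRP or white cells. Nowhere does the plan define change from Day 0, say which visits count, or say how to treat a patient already beyond a limit on Day 0.

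**The concern.** An outcome called an increase should describe something that happens after randomisation. A fixed limit does that only if patients start on the right side of it. The PaO₂/FiO₂ outcome in the same list has this protection: it counts values below 200, and entry requires a ratio above 200. CRP and white cells have no such protection.

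The plan itself expects inflammation at entry. Under Dosage and administration it says that patients have been ill for about a week when admitted and that the inflammatory response drives later complications. Some patients may therefore be above a limit before the first dose.

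If they count as events, similar totals in the two arms would largely reflect entry status but could be reported as no effect on inflammation. With about 20 per arm, a chance difference in entry status could equally be taken for a treatment effect.

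**Working it through.** **The plan's own figure.** No figure is given for these two outcomes. The only sample size is 40 followed patients, for viral load: 30% against 75%, 80% power, two-sided 5%. With pooled variance and no continuity correction,

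n per arm = [1.960 × √(2 × 0.525 × 0.475) + 0.842 × √(0.30 × 0.70 + 0.75 × 0.25)]² / 0.45² = 18.1, rounded up to 19.

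That is 38 in total, close to the stated 40. So 20 per arm is used below.

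**Inputs.**
- From the plan: 20 per arm (40 followed, 1:1) and Fisher's exact test.
- Assumed: b, the share above the limit on Day 0, equal in both arms. It is shown over a wide range because the documents do not give it.
- Assumed: new-onset rates of 75% and 30% among patients within the limit on Day 0. These borrow the plan's 45-point viral load contrast for illustration only.

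**Formula under an ever-above-the-limit rule.** A patient above the limit on Day 0 is an event whatever happens later, so in an arm with new-onset rate r:

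observed rate = b + (1 − b) × r

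observed difference = (1 − b) × (0.75 − 0.30) = 0.45 × (1 − b)

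Power is exact, found by enumerating all tables with Fisher p ≤ 0.05. The last two columns give the alternative count, restricted to patients within the limit on Day 0, which keeps the 75% against 30% contrast.

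| b (assumed) | Observed rates, literal count | Difference (points) | Power, 20 per arm | At risk per arm | Power, at-risk count |
|---|---|---|---|---|---|
| 0 | 75% vs 30% | 45 | 0.73 | 20 | 0.73 |
| 0.2 | 80% vs 44% | 36 | 0.56 | 16 | 0.62 |
| 0.5 | 87.5% vs 65% | 22.5 | 0.28 | 10 | 0.33 |
| 0.8 | 95% vs 86% | 9 | 0.055 | 4 | 0.08 |
| 0.9 | 97.5% vs 93% | 4.5 | 0.01 | 2 | 0 |

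**What the two counts can show at b = 0.8.** With 16 of 20 per arm abnormal at entry, the most extreme literal result is 20/20 against 16/20, Fisher p = 0.106. Among the 4 per arm at risk, 4/4 against 0/4 gives p = 0.029. At this share the literal count would hide complete separation.

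**Limit of the at-risk count.** At b = 0.9, with 2 per arm at risk, 2/2 against 0/2 gives p = 0.33. Restricting the count makes it mean what its name says, but restores little power when b is high. That is why a continuous analysis should come first.

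**The case against.** The strongest reply is that the plan never says entry abnormality counts. The list speaks of *altered* sodium and potassium, a state, but of *increase*, *deterioration* and *worsening* elsewhere, which suggest change. On that view an increase is a rise from Day 0 that passes the bracketed limit. This reading is not excluded. It is not secured either: the same list has "Pancreatitis characterized by increase in amylase >200 U/L", which gives only a level. What stands is that the rule is unwritten. A reader might infer that the plan definitely counts entry abnormality as an on-study event, but the documents support this only as the result of one literal reading.

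A reader might also infer that these outcomes cannot respond to treatment or reach significance. That holds only if any visit above the limit counts. If the count were taken on Day 8, values could fall back: with 18/20 above the limit in each arm on Day 0 (assumed), Day 8 counts of 18/20 against 10/20 give Fisher p = 0.014.

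Nor do the documents show that most patients start above either limit. Abnormality at entry may matter more for CRP than for white cells, but that too is an assumption.

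Finally, numeric values are recorded and rank tests for continuous and paired data are named, so part of the remedy is within reach. That is fair, but those tests are not assigned to these markers, and no Day 0 adjustment is specified.

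**Conclusion.** The point holds as a gap in definition with a conditional cost. Both outcomes are patient counts beyond an absolute limit, without a Day 0 reference or a visit rule. Under the ever-above reading, any true difference shrinks by the factor (1 − b): modestly at b = 0.2 and almost completely at b = 0.9. The size rests on three assumptions: the entry share, the borrowed 75% and 30% rates, and that reading of the outcome.

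It would be wrong to infer bias in favour of one arm. Entry status precedes treatment, so the expected effect is dilution, with chance imbalance between small arms on top. These are two unpowered secondary items; the primary outcomes and the sample size are untouched. This is a worthwhile improvement of low severity.

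**What to change.** In the statistical analysis section, make the main comparison for both markers continuous: CRP on the log scale and white cell count, on Days 2, 5, 7 and 8, between arms and adjusted for each patient's Day 0 value.

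If a count is also reported:
- define it as a new crossing of the limit among patients within it on Day 0;
- name the visits that count;
- show the Day 0 share above the limit by arm;
- treat the result as descriptive, because few patients may be at risk.

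The cost is analysis wording only. Day 0 and later values are already scheduled and recorded as numbers, so no visit, sample or participant is added. The wording should be fixed before unblinding, so that the counting rule is not chosen after the results are known.

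### The PaO2/FiO2 deterioration outcome puts its cut-off on the entry line and asks for no fall from Day 0, so it misclassifies patients and loses sensitivity to respiratory worsening

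*Combined protocol and SAP*

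**What the plan says.** Under Secondary objectives assessment, the safety findings are to be reported "in number of patients, and hospitalization days". One of the 16 listed items is "Deterioration of arterial blood gas paO₂/pFiO₂ ratio (<200".

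Under Eligibility criteria, patients must have a "gas exchange ratio >200 in blood gas analysis (paO₂ / pFiO₂), characterizing mild hypoxemia". No numeric upper limit is given.

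The schedule (Interventions and inpatient schedule, Table 1) has a row for "Complete blood count, D-dimer, aPTT, urea, creatinine, glucose, reactive protein C, blood gas and amylase", marked on Days 0, 2, 5, 7 and 8. That is one baseline reading and four later ones. The laboratory form (Assessment forms, Figure 3) has a field for the numeric ratio.

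Under Sample size, recruiting and statistical analysis, "Categorical variables will be evaluated with Fisher's exact test". The same paragraph names Mann-Whitney for continuous variables and Wilcoxon for paired comparisons, without tying either to an outcome. For the gas-exchange outcome the documents state no minimum change from Day 0, no confirmatory reading, no assessment day and no adjustment for the starting value.

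**The concern.** The outcome is named as a deterioration, which is a change, but it is defined as a level. Because that level is also the entry limit, whether a patient counts depends heavily on where they started. Someone a few points above 200 needs only a trivial or purely random drop, and has four chances to show one. Someone well above 200 can worsen substantially and stay uncounted.

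The item is one of the plan's respiratory safety measures, and the study design section gives safety as the main intention. With about 20 patients per arm, a count that mixes noise with real worsening and misses real falls from higher values may fail to show respiratory harm that the same blood gases could reveal.

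**Working it through.** The plan gives no event rate, effect size or power for this outcome, so there is no figure of its own to reproduce. The only design number used is the 40 patients to be followed, randomised 1:1: 40 / 2 = 20 per arm.

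**Step 1: fall needed to reach 200 (no assumptions).** For a Day 0 ratio B the fall is (B − 200) / B.

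| Day 0 ratio | Fall to reach 200 |
|---|---|
| 201 | 1/201 = 0.5% |
| 210 | 10/210 = 4.8% |
| 250 | 50/250 = 20% |
| 300 | 100/300 = 33.3% |
| 400 | 200/400 = 50% |

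A drop from 300 to 201 is 99/300 = 33.0% and is not an event. A drop from 201 to 199 is 1.0% and is one.

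**Step 2: noise in one patient whose true ratio does not change.** Assume normal within-patient error with SD s, independent between readings. One reading falls below 200 with probability p = Φ((200 − B)/s), and at least one of four does so with probability 1 − (1 − p)^4. The documents give no SD; 15, 25 and 35 are assumed.

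- B = 210: z = −0.67, −0.40, −0.29; p = 25%, 35%, 39%; at least one of four = 69%, 82%, 86%.
- B = 250: z = −3.33, −2.00, −1.43; p = 0.04%, 2.3%, 7.7%; at least one of four = 0.2%, 9%, 27%.

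**Step 3: noise across a trial population.** Simulation with no true change in anyone: true ratio uniform over an assumed range, Day 0 reading required to exceed 200, four later readings, event if any is below 200.

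| Assumed true range | SD 15 | SD 25 | SD 35 |
|---|---|---|---|
| 200 to 300 | 12% | 21% | 31% |
| 200 to 400 | 6% | 10% | 14% |

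The entry range matters as much as the SD: widening it to 400 roughly halves the rate.

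**Step 4: does the noise create false differences between arms?** With 20 per arm, equal event rates of 12.3%, 21.3% or 31.3%, and Fisher's exact test at two-sided 5%, the chance of p ≤ 0.05 is 1.6%, 2.3% or 2.5%. This is below nominal.

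**Step 5: sensitivity to a real difference.** Same model (200 to 300), 20 per arm, with a true 10% fall at every later visit in one arm only. The ranges are over repeated simulation runs.

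| Analysis | SD 15 | SD 25 | SD 35 |
|---|---|---|---|
| Count below 200, Fisher's test | 30% | 26–28% | 24–25% |
| Day 8 ratio, Day 0 as covariate | 97–98% | 67–72% | 46–47% |

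The second analysis uses a single later reading and still detects the fall about two to three times as often. The model has complete data and normal errors, which favours it somewhat.

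**The case against.** The strongest defence is that the shared line is deliberate. The eligibility text treats a ratio above 200 as mild hypoxaemia, so a reading below 200 means leaving the severity class in which the patient was enrolled. That is a legitimate and readable safety count. This stands, and it is the reason to keep the count. It does not make the count a sensitive comparison between arms.

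It can also be said that the numeric ratio is recorded and rank tests are listed, so a continuous analysis is already possible. It is possible, but not specified: the test list is generic, and the only stated form of this outcome is the number below 200.

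This is also one secondary item among 16, with no power claim and no primary conclusion resting on it. That limits its importance.

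Several stronger readings are tempting, but the documents do not support them:

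- **That the definition biases the comparison or manufactures an effect.** Randomisation and blinding make the noise the same in both arms in expectation, and step 4 shows no excess of false positives.
- **That the count mainly reflects how many patients entered near 200.** In the 200 to 300 model, patients with a Day 0 reading of 200 to 225 (about a fifth of the total) supply about 72% of false events at SD 15, but only about 46% at SD 25 and 32% at SD 35.
- **That patients at 400 are typical.** They meet the literal criterion, but the mild-hypoxaemia wording may make them uncommon. The case from 300 is enough.
- **That nebulisation distorts the ratio.** The solution is "administered in a source of oxygen or compressed air (5L/min or according to" need, and no draw time is set. However, both arms follow the same nebulisation schedule and nothing says that gases are drawn during it. This is an operational detail.

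**Conclusion.** The concern holds as a weakness in how one secondary safety outcome is defined and analysed. The shared cut-off, the absence of a required fall and the four later readings are all in the text, and the percentages in step 1 need no assumption.

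The false-event rates (12% to 31%, or 6% to 14% with the wider entry range) and the detection rates in step 5 depend on the assumed SD, the assumed entry distribution and independent errors. They show the order of magnitude and are not predictions for this trial. Because the false-event model contains no true change, it also cannot say what share of the events eventually observed would be noise. The consequence is misclassification and lost sensitivity with about 20 per arm, not systematic bias. The point should be addressed, and that can be done in the analysis plan alone.

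**What to change.** Make the main gas-exchange analysis a between-arm comparison of the recorded PaO2/FiO2 at a stated day (for example Day 8, or across the scheduled days), with each patient's Day 0 value as covariate. Keep the number of patients below 200 as a descriptive count of change of severity class, reported alongside the Day 0 values.

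A reader might prefer to add a minimum percentage fall, such as 20%, to the count. That is not advised. The figure has no source in the documents, the combined rule would still miss a fall from 400 to 210, and it would drop a fall from 210 to 175 (35/210 = 16.7%). At SD 35 it would only cut false events from 31% to 23%.

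The cost is a little more analysis work, plus a stated way to handle patients who die, are ventilated or leave before the chosen reading. That rule is needed because such patients may be the ones who worsened. No extra tests, visits or form fields are required.
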